Specific Aim #1: Determine the Clinical effects of rTMS combined with BoNT in isolated cervical dystonia. We will determine the clinical effects of active vs. sham rTMS on motor, non-motor, and gait symptoms. We will examine the motor effects with the standardized Toronto Western Spasmodic Torticollis Rating Scale (TWSTRS), mood with the Beck Depression Inventory, cognition with the Wisconsin Card Sorting Task and Trail Making Test, and gait with the instrumented Zeno walkway system. We hypothesize there will be greater improvement in the motor (primary outcome), nonmotor, and gait measures (secondary outcomes) at T1, and T2 compared to baseline in the active rTMS group compared to the sham rTMS group.

Specific Aim #2: Determine the Physiological effects of rTMS combined with BoNT in isolated cervical dystonia. We will determine the physiological effects of active vs. sham rTMS using TMS and EEG techniques. We will examine the cortical excitability with established TMS parameters including MEP, CSP, and SICI, and we will examine cortical desynchronization of alpha and beta band with resting state HD-EEG. We hypothesize that the change in TMS measures and EEG measures at T1, and T2 compared to baseline will significantly improve in the active rTMS group compared to the sham rTMS group and will correlate with the clinical improvements as outlined in specific Aim #1.

[figure not shown]
RESEARCH PLAN AND METHODOLOGY: Patients with a diagnosis of isolated cervical dystonia receiving BoNT every 12 weeks at our movement disorders center will be enrolled. Diagnosis of cervical dystonia will be established in accordance with the Consensus Statement of the Movement Disorders Society.¹

Inclusion Criteria: patients 18-85 years of age who receive regular BoNT scheduled every 12 weeks, on stable optimized doses but with reported benefits lasting \leq 9 weeks for 2 consecutive cycles. Patents followed at our center routinely fill out a self-reported form to document the duration of benefits perceived with BoNT therapy. Participants will be allowed to continue oral medications that they are taking for dystonia concurrently and will be encouraged to continue this regimen throughout the duration of the study .

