Primary Outcome: Motor symptoms of dystonia will be measured with TWSTRS; a widely accepted composite rating scale for cervical dystonia with subscales for clinical severity, functional disability, and associated pain. We will record videos of subjects at baseline and follow-up time points, which will be scored by two independent blinded raters.

Secondary Outcomes: Non-motor symptoms will be measured as follows: mood with the Beck Depression Inventory (BDI) and cognitive tasks as measured by the Wisconsin Card Sorting Task (WCST) and Trail Making Test (TMT); gait with Zeno walkways system for temporal parameters (stance time, double support time, stride time, and cadence), spatial parameters (stride length, step width, step length, step asymmetry), and the dynamic stability index (ratio between single and double support time)^{4,5}; physiological outcomes will be measured with standard procedures for TMS based MEP, CSP, and SICI²⁵⁻³⁰ and HD-EEG based power of alpha and beta bands during resting state.³¹

Randomization: A random number generator will be used to assign patients to active or sham stimulation during the S1 time period. If the number is even, the patient will be assigned active stimulation. If the number is odd, the patient will be assigned sham stimulation. The study team member who makes these assignments will be aware of which patients are receiving active or sham stimulation but will be different from the blinded reviewer. The blinded reviewer will be unaware of the patient's assignment to active or sham stimulation. Following crossover, the patients will undergo whichever treatment condition (active or sham) they were not exposed to during S1.

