Trail-Making Test: This is a 2-part evaluation in which patients are instructed to connect circles in ascending numerical order and are scored on how quickly they are able to complete the task.

Wisconsin Card Sorting Test (WCST): This is a cognitive task that asks patients to sort cards based on color, number, and shape.

Gait Assessment: Patients will be asked to walk across the Zeno walkways system for temporal parameters (stance time, double support time, stride time, and cadence), spatial parameters (stride length, step width, step length, step asymmetry), and the dynamic stability index (ratio between single and double support time). This portion of the study will be videotaped.

Patient will also have HD-EEG and TMS measures (MEP, CSP, and SICI) performed as described above.

Patients will have primary and secondary outcome measures performed at six timepoints: Baseline (T0), following rTMS (T1), and 2 weeks following rTMS (T2) during session 1 (S1) and baseline (T0), following rTMS (T1), and 2 weeks following rTMS (T2) during session 2 (S2) (Figure 1). The study protocol will take place over approximately 24 weeks. All events related to the study procedure will take place within +/- 14 days of the expected timeline, with more details below (Table 1).

Table 1. Timeline of study events and expected study activities at each timepoint.

	Session	S1					\$2				
Study Events (to occur +/- 14 days)	Screen- ing	Botox- Week 0	Baseline (T0)- Week 9	rTMS protocol (4 days)	Post- TMS (T1)- Week 10	2 weeks post- TMS (T2)- Week 12	Botox- Week 12	Baseline (T0)- Week 21	rTMS protocol (4 days)	Post- TMS (T1)- Week 22	2 weeks Post- TMS (T2)- Week 24
Informed											
Consent											
Medical History											
Neurologic Exam											
Pregnancy Test (if woman of childbearing age)											
Demographic											
S											
Botox											
Active or Sham rTMS											
TWSTRS											
BDI											
Trail Making Test											
WCST											
MEP											
CSP											
SICI											
Gait											
assessment											
HD-EEG											
Study Compensatio n											

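### Practice on the cognitive tests over six visits is an unmodelled period effect: it adds noise and chance bias of either sign to the active-versus-sham contrast, and obscures change from baseline within a condition

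*Protocol*

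**What the plan says.** The protocol (Secondary Outcomes) lists the Wisconsin Card Sorting Task and the Trail Making Test as its cognitive measures. Under Clinical Assessments it states "Patients will have primary and secondary outcome measures performed at six timepoints": T0, T1 and T2 in each of two sessions. Table 1 places these at about weeks 9, 10 and 12, then 21, 22 and 24, starting from "Baseline (T0)- Week 9". The window is wide: "All events related to the study procedure will take place within +/- 14 days of the expected timeline".

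On the Trail Making Test, patients are "scored on how quickly they are able to complete the task". The card-sorting entry reads "This is a cognitive task that asks patients to sort cards based on color, number, and shape". Neither entry names a version or form, or mentions a practice run.

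Specific Aim #1 expects greater improvement in "nonmotor, and gait measures (secondary outcomes) at T1, and T2 compared to baseline in the active rTMS group", and the comparator is the sham condition. The Randomization section assigns the first condition by whether a random number is even or odd, without blocking, for a target of 10 patients. The SAP gives a two-way repeated measures ANOVA for primary and secondary outcomes, with Benjamini-Hochberg control for the secondary ones. It does not name the two factors and mentions neither period nor sequence.

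**The concern.** A timed task and a rule-finding task can both be learned by repetition. Here each is taken six times, twice within about a week at the start of each session. A practice gain from T0 to T1 is part of the change score, so subtracting T0 does not remove it.

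Two things follow. First, improvement within a condition, and the time effect of the ANOVA, cannot be attributed to stimulation. Second, if patients gain more from practice in one session than in the other, the difference is a period effect. A two-period crossover protects the treatment contrast from a period effect when the sequences are equal in size or when period is modelled. The plan states neither. At stake is the reading of the cognitive secondary outcomes only.

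**Working it through.** **Inputs from the documents.** There are 2 sessions × 3 time points = 6 administrations. T0 to T1 is 10 − 9 = 1 week in session 1 and 22 − 21 = 1 week in session 2. From S1:T2 to S2:T0 is 21 − 12 = 9 weeks. The target is 10 patients with unblocked even/odd allocation. The sample size has no derivation to reproduce, because the protocol describes an unpowered pilot.

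**Assumed.** Let g1 and g2 be the mean T0-to-T1 practice gains in sessions 1 and 2, and D = g1 − g2. The documents give no value. D is taken from 0 to 1.0 SD, where the SD is that of a patient's active-minus-sham difference. Tests are two-sided at 0.05 (also assumed).

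**Bias.** Let τ be the true effect.
- Active-first patient: difference = (τ + g1) − g2 = τ + D.
- Sham-first patient: difference = (τ + g2) − g1 = τ − D.
- Mean over 10 patients = τ + (nAS − nSA)/10 × D.

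The same algebra holds for T0 to T2, with its own D.

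**How often the sequences are unequal** (binomial, n = 10, p = 0.5):

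| Split, either way | Probability | Size of bias |
|---|---|---|
| 5:5 | 252/1024 = 0.246 | 0 |
| 6:4 | 420/1024 = 0.410 | 0.2 D |
| 7:3 or worse | 352/1024 = 0.344 | 0.4 D or more |
| 8:2 or worse (within the row above) | 112/1024 = 0.109 | 0.6 D or more |

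The sign depends on which sequence is larger. The expected bias over the randomisation is zero.

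**Noise at 5:5.** Each difference carries +D or −D, so the expected sample variance is 1 + D² × 10/9. For D = 0.5 this is 1.278 (SD 1.13); for D = 1.0 it is 2.111 (SD 1.45).

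**Simulation** (100,000 runs per case). A paired t-test with no period term is compared with a period-adjusted crossover t-test.

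Power at 5:5 for a true effect of 1 SD:

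| D | No period term | Period term |
|---|---|---|
| 0 | 0.80 | 0.79 |
| 0.5 | 0.72 | 0.79 |
| 1.0 | 0.48 | 0.79 |

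Type I error given the split, no period term:

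| D | 5:5 | 6:4 | 7:3 | 8:2 |
|---|---|---|---|---|
| 0.5 | 0.030 | 0.037 | 0.061 | 0.106 |
| 1.0 | 0.007 | 0.016 | 0.063 | 0.200 |

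With a period term, type I error is 0.049 to 0.052 for every split from 5:5 to 8:2 and every D tried. Without one, averaged over the random sequence, it is 0.049 to 0.052.

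**The case against.** The strongest reply is that the hypothesis compares active with sham, every patient has both in random order, and practice raises both. That stands. A reader might infer that practice pushes the result towards active stimulation; the documents do not support this. The expected bias is zero, its sign in a given sample can go either way, and the averaged type I error stays close to 0.05. What remains is the bias for the split that actually occurs and the loss of power even at 5:5.

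A second reply is that much of the mechanism is unsourced, and this also stands. The documents name the same tests at each visit but do not say that identical forms are reused. They give no figure showing that the gain is larger in session 1 or that patients reach a ceiling in session 2, and the nine-week gap could allow some practice to fade. Hence D is an assumption with a range, and its lower end is no effect at all.

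Third, the two ANOVA factors are unnamed. If one were session, period would be partly represented, but the text does not say so. The cell marks of Table 1 are not legible in the text available, so the schedule here rests on the six-timepoint sentence. If the table shows the Trail Making Test at screening, part of the remedy is already in place.

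Finally, these are secondary outcomes with false discovery rate control in a pilot. That limits the importance, although multiplicity control does not address a period effect.

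**Conclusion.** The point holds as a modest, inexpensive improvement. The plan repeats two learnable tests six times and states no safeguard against practice. As a result, within-condition cognitive change cannot separate practice from treatment. Any between-session difference in practice gain enters the active-versus-sham contrast as chance bias of 0.2 D at 6:4 and 0.4 D at 7:3, and as extra variance at every split short of all patients sharing one sequence. For an assumed D of 0.5 SD, power at 5:5 falls from about 0.80 to 0.72; for 1.0 SD, to 0.48. If D is zero, the contrast is unharmed and only the within-condition reading is affected.

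It would go too far to conclude that the cognitive comparison systematically favours active stimulation, or that a session 2 ceiling hides a true effect. The first contradicts the crossover comparison in Specific Aim #1, and the second needs a practice figure that the documents do not give. The TWSTRS primary outcome is not touched.

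**What to change.** 1. Give the Trail Making Test once, unscored, at the existing screening visit.
2. Use alternate Trail Making forms, name them, and balance form order across patients equally within each sequence.
3. Add a period term to the analysis of the cognitive outcomes, and report the sequence split that occurred.
4. State that cognitive conclusions rest on the active-versus-sham difference, not on change from baseline within a condition.

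Do not add an unscored card-sorting run. It would remove the novelty of the task before the first scored visit; the period term has to do the work there.

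**Cost.** A few minutes at screening, possible small differences in difficulty between forms, and one degree of freedom. At 5:5 with D = 0 the period term costs little (power 0.80 to 0.79). It costs more when the split is unequal: simulated power with the term is about 0.72 at 7:3 and 0.60 at 8:2, because the smaller sequence limits precision. The split should therefore be shown beside the result.

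The SAP is written in the past tense. If data collection is complete, items 3 and 4 and disclosure of the forms used remain possible at almost no cost.

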NCT04916444

Title: Dystonia Treatment With Injections Supplemented By Transcranial Magnetic Stimulation

Document Date: 7/21/2024

The primary outcome was the Toronto Western Spasmodic Torticollis Rating Scale (TWSTRS). Participant exam was videotaped and the TWSTRS score was determined by two blinded raters who are fellowship-trained movement disorder neurologists. Secondary outcomes included non-motor symptoms such as mood measured by the Beck Depression Inventory (BDI), cognitive tasks measured by the Wisconsin Card Sorting Task (WCST) and Trail Making Tests (TMT A and B), and gait measured by the Zeno walkways system. In addition, patient-reported outcomes were collected regarding adverse events, tolerability, and predictions regarding the active versus the sham coil.

Two-way repeated measures ANOVA was used for statistical analysis of the primary and secondary outcomes. The statistical analyses were performed using SPSS. The Benjamini-Hochberg procedure was applied to control the false discovery rate for multiple comparisons of the secondary outcomes.

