Exclusion Criteria: 1) Presence of metallic objects or neurostimulators in the brain (including the following: cochlear implants, implanted electrodes/stimulators such as deep brain stimulators and vagus nerve stimulators, aneurysm clips or coils, stents, bullet fragments, jewelry and hair barrettes), 2) pregnancy, 3) history of active seizures or epilepsy, 4) patients with severe scoliosis or other gait impairment that will preclude them from participating in gait evaluation.

Enrollment: Our target is to enroll 10 total patients in the study in a crossover design, with all 10 patients receiving both active and sham rTMS in blinded, random order. In order to enroll 10, we will need to screen more than that number. We anticipate that we will need to screen 20 patients in order to find 10 that are eligible for enrollment. Of those 20, we anticipate that 10 will enroll but later choose not participate in the study.

IRB202101156 6/17/22 IRB approved informed consent will be obtained. The study procedures will be explained, and subjects will have a detailed medical history and neurological examination. Patients will be randomly assigned to receive either active or sham stimulation first (S1), and will then crossover and switch to the other treatment type during the second session (S2). Patients will have primary and secondary outcome measures performed at three time points: Baseline (T0), following rTMS (T1), and 2 weeks after rTMS (T2) (Figure 1). Patients will have the next round of regularly scheduled botulinum toxin injections during the T2 study visit, after the outcome measures have been obtained. Then the entire study protocol will be performed again but the patients will undergo either active or sham rTMS during S2 (whichever option they were not exposed to during S1). The study protocol will take place over approximately 24 weeks. Details of specific parts of the protocol are included below.

at baseline/9 weeks after BoNT (S1:T0), after the full rTMS protocol (S1:T1), and 2 weeks after rTMS (S1:T2). At the T2 visit, patients will be due for their next round of BoNT and will receive it at that time. Patients will have S2:T0 performed 9 weeks following this round of BoNT and will crossover into either active or sham rTMS (whichever condition they did not undergo in S1). Outcomes will be measured immediately following rTMS (S2:T1) and 2 weeks after rTMS (S2:T2).

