study.Childbearing Potential- There may be unknown risks to the fetus. Therefore, women of childbearing age will complete a pregnancy test for the TMS portion of the study at each visit. In order for the women of childbearing age to participate in this study, the participant should avoid becoming pregnant from their first day of most recent menses. A negative pregnancy test does not absolutely prove that a woman is not pregnant. If the female participant thinks that there is a possibility that she might be pregnant, the study team should be notified immediately. Nursing mothers are not eligible for participation in this project. The possibility exists that complications and undesirable side effects, which are unknown at this time, could occur.

EEG:

• A gel paste is used to attach the sensors during EEG which may mildly and briefly irritate the skin on the scalp or face. Hair products cannot be used on the day of testing (or should be washed out prior to testing), which may be inconvenient to the participant.

Possible Benefits: The participant may or may not benefit from taking part in the study. All participants will continue receiving botulinum toxin injections every 12 weeks as part of their standard of care. All patients will receive both active and sham rTMS; since the active rTMS is hypothesized to augment the effects of botulinum toxin injections, patients may experience further reduction in symptoms or sustained response to botulinum toxin. The information gathered from this study will benefit the neurology department and the larger research community as we continue to seek the most efficacious treatments for cervical dystonia.

Regulatory Approval and Statistics: The study will be approved by the University of Florida Institutional Review Board, and all subjects will provide written informed consent. The study is highly feasible given the relatively large number of patients with cervical dystonia that receive botulinum toxin injections on a regular basis. This is a pilot study so it has not been powered for statistical significance. We will use descriptive statistics and ANOVA to run analysis on the data that has been collected.

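### The SAP states no period or sequence term, and no supporting analysis, for a two-session crossover with unblocked order, so the active–sham estimate may carry part of any session difference in response

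*SAP*

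**What the plan says.** **Design.** Under Enrollment, the protocol targets 10 patients, each receiving both conditions: "Patients will be randomly assigned to receive either active or sham stimulation first (S1), and will then crossover". Each session has its own T0, T1 and T2; the visit schedule before Table 1 says "Patients will have primary and secondary outcome measures performed at six timepoints". The second baseline follows a new injection round: "Patients will have S2:T0 performed 9 weeks following this round of BoNT".

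**Order.** The Randomization paragraph uses a random number generator: "If the number is even, the patient will be assigned active stimulation". An odd number gives sham first. No block or fixed ratio is stated.

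**Hypothesis.** Specific Aim #1 expects "greater improvement in the motor (primary outcome), nonmotor, and gait measures (secondary outcomes) at T1, and T2 compared to baseline" under active rTMS than under sham.

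**Analysis.** The last paragraph of the SAP says "Two-way repeated measures ANOVA was used for statistical analysis of the primary and secondary outcomes". It adds the software and a false-discovery-rate procedure for the secondary outcomes. It does not name the two factors or say which ANOVA effect is the test. The protocol (Regulatory Approval and Statistics) says only "We will use descriptive statistics and ANOVA to run analysis on the data that has been collected" and notes "This is a pilot study so it has not been powered for statistical significance". Neither document mentions a period, session, sequence or carryover term, or a supporting analysis.

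**The concern.** The Aim 1 comparison needs a treatment factor and a visit factor, and these use up both ways of a two-way ANOVA. Treatment by period could not be two fully crossed within-patient factors, because each patient fills only two of those four cells. The natural reading is therefore treatment by visit, with no period in the model.

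In a two-period crossover, an unmodelled period effect on the outcome contrast drops out of the treatment estimate only if the two sequences are equal in size. Here equal sizes are left to chance. One possible source is practice on the Wisconsin Card Sorting Task and Trail Making Test, each given six times: the gain from T0 to T1 could be larger in the first session than in the second. At stake is the effect estimate, which is the main product of an unpowered pilot.

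**Working it through.** The plan contains no power or precision calculation to reproduce. The only planned figure is the target of 10 patients.

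**Inputs from the documents:** 10 patients, two sessions, T0/T1/T2 in each, unblocked order.

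**Assumptions:** probability 0.5 for each order; 10 complete patients; two-sided 5% level; variances 0.5 (patient), 0.25 (patient-by-period) and 0.25 (residual), for a total SD of 1; session differences from 0 to 1 SD; treatment effect 0.8 SD.

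**1. What cancels.** Let π be the S2-minus-S1 difference in the change from T0, τ the treatment effect on that change, nAB the number with active first and nBA the number with sham first. The active-minus-sham change has mean τ − π with active first and τ + π with sham first. A constant session shift appears at T0 as well as at T1 and T2, so it drops out. Over all patients:

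E[mean active-minus-sham change] = τ + π(nBA − nAB)/10.

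**2. Scale.** The variance of this contrast is 4 × 0.25 = 1.0 (SD 1.0) for one visit, and 2 × (0.25 + 0.125) = 0.75 (SD 0.866) for the average of T1 and T2 minus T0.

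**3. Split, bias and cost.** Split probability is C(10,5)/1024 for 5:5 and 2·C(10,k)/1024 for k > 5. The adjusted estimate is the mean of the two sequence means. Its variance relative to the unadjusted estimate is 10(1/nAB + 1/nBA)/4. Its interval width ratio is (2.306/2.262) × the square root of that, because degrees of freedom fall from 9 to 8. The type I error columns are for the unadjusted one-sample t-test on the single-visit change, by simulation, at session differences of 0.25, 0.5 and 1 SD.

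| Split | Probability | Share of π in estimate | 0.25 SD | 0.5 SD | 1 SD | Variance ratio | Interval ratio |
|---|---|---|---|---|---|---|---|
| 5:5 | 0.246 | 0% | 4.4% | 3.0% | 0.7% | 1.00 | 1.02 |
| 6:4 | 0.410 | 20% | 4.6% | 3.7% | 1.6% | 1.04 | 1.04 |
| 7:3 | 0.234 | 40% | 5.3% | 6.1% | 6.4% | 1.19 | 1.11 |
| 8:2 | 0.088 | 60% | 6.6% | 10.6% | 20.1% | 1.56 | 1.27 |

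The remaining splits are 9:1 (probability 0.020, share 80%, interval ratio 1.70) and 10:0 (0.002, share 100%, adjusted estimate not available). Equal sequences therefore have probability 0.246 and unequal ones 0.754.

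At 5:5 there is no bias, but π enters the error term. With π = 0.5 the expected sample variance of the contrast rises from 1.00 to 1.00 + 10 × 0.25/9 = 1.28, which is why the test becomes conservative.

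Averaged over allocation, the unadjusted t-test has type I error of 5.0% to 5.2%. The adjusted test holds about 5% at every split from 5:5 to 9:1.

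**4. Check on the ANOVA itself.** In a simulated treatment-by-visit ANOVA, a constant session shift of 1 residual SD left the interaction F test at 5.1%, 5.2%, 5.1% and 4.9% for 5:5 to 8:2. The same shift at T1 and T2 only gave 3.1%, 3.9%, 6.1% and 10.8%. That shift is 0.5 SD of the single-visit contrast (whose SD is √4 = 2 residual SDs), so it agrees with the 0.5 SD column.

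**5. Power for a 0.8 SD effect, averaged over allocation.**

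| Session difference | Single-visit t, unadjusted | Single-visit t, adjusted |
|---|---|---|
| 0 | 61.6% | 55.7% |
| 0.25 SD | 59.0% | 55.7% |
| 0.5 SD | 52.1% | 55.7% |
| 1 SD | 34.5% | 55.7% |

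With the treatment-by-visit F test at 0.5 SD, the figures are 58.3% unadjusted and about 60.7% adjusted, a gain of about 2 points. With 8 patients (assumed) they are 46.9% and 47.5%.

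**6. Check on the proposed model.** In one simulated complete data set at 7:3 (true effect 0.8, π = 0.5), the mixed model's treatment-by-visit estimates were 0.531 (T1) and 0.560 (T2), equal to the mean of the two sequence means. The unadjusted means were 0.379 and 0.377. The expected unadjusted bias was 0.5 × (3 − 7)/10 = −0.2.

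**The case against.** The SAP's statistical text is very short and names no factors, so its silence does not prove that period was left out. That stands: the documents support saying that no such term is stated, not that one was excluded.

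The design already removes the ordinary period effect, because each session has its own T0 nine weeks after its own injections. That also stands, and leaves only a session difference in response. The documents give no evidence of one. Practice is plausible for the cognitive tests but a weaker candidate for TWSTRS, which blinded raters score from video. The 14-day visit window adds scatter, but nothing in the documents makes it differ systematically between sessions.

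A reader might infer that the planned test has an inflated false-positive rate, or that the ANOVA is invalid and should be replaced. The figures do not support this. The unadjusted t-test is conservative at 5:5 and 6:4 (66% of allocations). It is clearly inflated only at 8:2 or worse (probability 0.109), and then only if the session difference is substantial; the 20% figure needs a difference larger than the assumed treatment effect. Adjustment loses average power at 0 and 0.25 SD.

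What survives is that readers see one realised split, not the average over allocations. Without sequence counts or an adjusted estimate, they cannot tell whether the result depends on order.

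**Conclusion.** The point holds as a minor one. For a crossover with unblocked order, the plan states no period or sequence term and no analysis that would show whether the result depends on order. Given the split, the active–sham change estimate carries 0%, 20%, 40% or 60% of any session difference in response at 5:5, 6:4, 7:3 or 8:2. At 5:5 the cost is precision instead of bias.

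The shares follow from the design and 10 complete patients. The type I error and power figures are mostly t-test approximations under assumed variances, session differences and effect size. The documents give neither the realised split nor the number analysed; 10 is a target. It therefore cannot be said that the reported result is biased, or in which direction. Because the trial is a pilot not powered for significance, the point bears on the effect estimate more than on the test.

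**What to change.** Keep the two-way ANOVA and state its two factors and the effect tested. Beside it, for TWSTRS and the secondary outcomes, report a linear mixed model on the T0, T1 and T2 scores (SPSS MIXED) with:

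- fixed effects for treatment, visit, treatment-by-visit, period and period-by-visit;
- random patient and patient-within-period effects;
- small-sample degrees of freedom.

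Give the treatment-by-visit contrasts (T1 − T0 and T2 − T0, active minus sham) with 95% intervals, and show the number of patients in each sequence. The SAP is written in the past tense, so label the model post hoc if it was not planned before the data were seen.

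**Cost.** One added procedure and a few lines of SAP text; no new data. In the simple contrast it uses one degree of freedom. With 10 complete patients, intervals are wider by about 2% (5:5), 4% (6:4), 11% (7:3) or 27% (8:2), and the adjusted estimate is unavailable at 10:0. With no session difference, single-visit power for 0.8 SD falls from about 62% to 60%, 59%, 53% or 43% at those four splits. That loss is why the model should support the ANOVA and not replace it.
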